Hyperphosphatemia	
Serum phosphate $\geq 5.5 - \leq 7$ mg/dL
 
Serum phosphate $> 7 - \leq 10$ mg/dL
 
Serum phosphate >10 mg/dL
	
Continue at the current dose and initiate phosphate lowering therapy. Monitor serum phosphate weekly.
 
• Initiate or adjust phosphate lowering therapy. Monitor serum phosphate weekly and Dose reduced to next lower dose
 
 - If the serum phosphate resolves to ≤ 7 mg/dL within 2 weeks after dose reduction, continue at this reduced dose. - If serum phosphate is not ≤ 7 mg/dL within 2 weeks, further reduce to the next lower dose. - If serum phosphate is not ≤ 7 mg/dL within 2 weeks after the second dose reduction, withhold until serum phosphate is ≤ 7 mg/dL and resume at the dose prior to suspending. 
Initiate or adjust phosphate lowering therapy and monitor serum phosphate weekly and
 
 • Withhold until phosphate is ≤ 7 mg/dL and resume at the next lower dose. - Permanently discontinue if serum phosphate is not < 7 mg/dL within 2

		weeks following 2 dose interruptions and reductions.
Other Adverse Reactions	Grade 3 ^a	Withhold until toxicity resolves to Grade 1 or baseline, then resume - for hematological toxicities resolving within 1 week, at the dose prior to suspending. - for other adverse reactions, at next lower dose.
	Grade 4 ^a	Permanently discontinue

^a Severity as defined by National Cancer Institute Common Terminology Criteria for Adverse Events (NCI CTCAE version 5.0).

Dose Modifications for Hematologic Toxicities are presented in [Table 5](#).

Table 5: Futibatinib Dose Interruption and Modification for Related Hematologic Toxicities

CTCAE Grade (value)	Recommended dose modification any time during a cycle of futibatinib ^a
Anemia (Hgb)	
Grade 1 (Hgb < LLN - 10.0 g/dL)	Maintain dose level
Grade 2 (Hgb < 10 – 8.0 g/dL)	Maintain dose level
Grade 3 (Hgb < 8.0 - 6.5 g/dL)	Withhold dose until resolved to ≤ Grade 1 or baseline, • If resolved ≤7 days, then maintain dose level • If resolved >7 days, then reduce 1 dose level
Grade 4 (life threatening consequences; urgent intervention indicated)	Withhold dose until resolved to ≤ Grade 1 or baseline, then reduce 1 dose level
Neutropenia (ANC)	
Grade 1 (ANC < LLN - 1500/mm ³)	Maintain dose level
Grade 2 (ANC < 1500 - 1000/mm ³)	Maintain dose level
Grade 3 (ANC < 1000 - 500/mm ³)	Maintain dose level

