Grade 4 (ANC < 500/mm ³)	Withhold dose until resolved to ≤ Grade 2 or baseline, • If resolved ≤7 days, then maintain dose level • If resolved >7 days, then reduce 1 dose level
Febrile neutropenia: ANC < 1000/mm ³ , and with a single temperature > 38.3°C (101°F) or a sustained temperature ≥ 38°C (100.4°F) for more than one hour.	Withhold dose until resolved, then reduce 1 dose level
Thrombocytopenia	
Grade 1 (PLT < LLN - 75,000/mm ³)	Maintain dose level
Grade 2 (PLT < 75,000 - 50,000/mm ³)	Maintain dose level
Grade 3 (PLT < 50,000 - 25,000/mm ³)	Withhold dose until resolved to ≤ Grade 1 or baseline, • If resolved ≤7 days, then maintain dose level • If resolved >7 days, then reduce 1 dose level
Grade 4 (PLT < 25,000/mm ³)	Withhold dose until resolved to ≤ Grade 1 or baseline, then reduce 1 dose level

Abbreviations: ANC=absolute neutrophil count; CTCAE=Common Terminology Criteria for Adverse Events; Hgb=hemoglobin; LLN=lower limit of normal; PLT=platelets.

a. Interrupt futibatinib if any toxicities are intolerable, regardless of the grade (including Grade 1 and 2). If or when the toxicity resolves to a tolerable state, consideration can be given to resuming futibatinib at the same dose if deemed appropriate or reduced by one dose level if needed.

Dose Modifications in Case of Induced Drug Liver Injury (Hy's Law)

Futibatinib will be permanently discontinued (pembrolizumab is allowed to be administered as a single agent if there is no tumor progression and no pembrolizumab related prohibitive toxicity) if liver function test abnormalities fulfill Hy's Law criteria defined as concurrent observation of the following, with no other reason found to explain the findings (such as viral hepatitis A, B, or C; preexisting or acute liver disease; liver metastases; or another drug capable of causing the observed liver injury):

- Elevated aminotransferase enzymes of $>3 \times$ ULN (upper limit of normal)
- Alkaline phosphatase (ALP) $<2 \times$ ULN
- Associated with an increase in bilirubin $\geq 2 \times$ ULN

Dose Delays and Interruptions Specific for Pembrolizumab

Description of Pembrolizumab: please see pembrolizumab packaging insert.

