Patients are not permitted to receive any other investigational or any other anticancer therapy, including chemotherapy, immunotherapy, biological response modifiers, or antineoplastic endocrine therapy during the study treatment period.

Extended-field radiation therapy or palliative radiation to a focal site of measurable disease is also prohibited. If it is deemed in the best interest of the patient and after discussion between the Investigator and Medical Monitor, it can be administered, but the patient will be censored for the primary endpoint analysis.

Immunosuppressive therapy including steroids (> 10 mg/day prednisone or equivalent) is not permitted with pembrolizumab.

Concomitant strong inhibitors and inducers and sensitive substrates of CYP3A4 should be avoided, if possible, with futibatinib. Caution is advised if these drugs are given concomitantly (see [Appendix A: CYP3A4 and Transporters – Classification of Substrates, Inhibitors, and Inducers of CYP Enzymes and Transporters](#)). Alternative replacement is highly recommended.

Concomitant Medications and Therapies Requiring Precautions

Supportive treatment is allowed based on available institutional or local guidelines.

Local or regional palliative cryotherapy or radiation, such as for bone pain or palliative surgery (non-anti-neoplastic intent), are permitted (provided the target lesion is not a site of measurable disease and is not indicative of disease progression). Study therapy should be ceased a minimum of 2 days prior to administration of palliative treatment, and may be resumed 7 days after the procedure or when the patient has recovered from the side effects of the procedure.

The following medications/therapies may be given concomitantly under the following guidelines:

Hematologic Support: may be administered as medically indicated (that is, blood transfusions, granulocyte colony-stimulating factor, erythropoietin stimulating agents) according to the institutional site standards or American Society of Clinical Oncology (ASCO) guidelines ⁷⁶.[76].

Management of Diarrhea: Prophylactic treatment for diarrhea is permitted during the study if clinically indicated according to the institutional or published guidelines ⁷⁷.

Management of Nausea/Vomiting: Antiemetics may be administered as clinically indicated according to institutional standards or ASCO guidelines ⁷⁸.

Drug Interactions

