5.6 Evaluation of Toxicity

This is an open-label phase II study. MD Anderson will have access to the Safety Data on a regular basis.

The lead-in patients have to be evaluated for DLT. The DLT window is 21 days.

Hematological DLT is defined as study drug-related toxicity:

- Platelets < 25,000 / μ L or bleeding associated with platelets < 50,000 / μ L
- Grade 4 neutropenia lasting 7 or more days
- Neutropenic fever

Non-hematological toxicities are graded using NCI CTCAE v5.0 toxicity criteria and the DLT is defined as study drug-related toxicity:

- Grade 3 or greater non-hematological toxicity other than nausea, vomiting, or fatigue
- Grade 3 or greater clinically significant electrolyte abnormalities
- Grade 3 nausea and vomiting related to study drug treatment that is not controlled at 72 hours despite appropriate antiemetic therapy
- Evaluation of liver toxicity as defined by Hy's Law:
 - The drug causes hepatocellular injury with ALT or AST \geq 3 x ULN or baseline
 - Total Bilirubin $>$ 2 x ULN, without initial findings of cholestasis (elevated serum alkaline phosphatase < 2 x ULN)
 - No other reason can be found to explain the combination of increased ALT/AST and total bilirubin, such as viral hepatitis, alcohol abuse, ischemia, preexisting liver disease, or another non-study agent capable of causing the observed injury
- Persistent Grade 2 toxicity or laboratory tests such as hyperphosphatemia or hypophosphatemia that cannot be resolved by administering phosphate binders, and requires a dose reduction will be considered a DLT if the treating physician and the principal investigator concur.
- Any death not clearly due to underlying disease or extraneous causes

The following types of toxic effects would not be considered in the definition of DLT:

- Alopecia, or nausea and vomiting in the absence of appropriate antiemetics, or insomnia, obesity/weight gain, infertility, amenorrhea, galactorrhea, or glucose intolerance that is believed to be due to dexamethasone used as antiemetic.
- The laboratory tests if asymptomatic despite being Grade 3, except for phosphate levels as described above.

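### As written, uncontrolled Grade 3 vomiting is a DLT but isolated Grade 4 vomiting is not (minor drafting inconsistency in section 5.6)

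*Combined protocol and SAP*

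**What the plan says.** Section 5.6 holds the only DLT definition. Sections 4.1, 7.1 and 7.3 use the term without redefining it.

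- **General non-hematological criterion:** "Grade 3 or greater non-hematological toxicity other than nausea, vomiting, or fatigue".
- **The one bullet that brings vomiting back:** "Grade 3 nausea and vomiting related to study drug treatment that is not controlled at 72 hours despite appropriate antiemetic therapy".
- **Other non-hematological criteria:** Grade 3 or greater clinically significant electrolyte abnormalities; Hy's Law liver injury; persistent Grade 2 toxicity or phosphate-type laboratory problems, if the treating physician and principal investigator agree; and any death not clearly due to other causes.
- **Events not considered DLTs:** nausea and vomiting appear only where appropriate antiemetics were not given. Laboratory findings are covered by "The laboratory tests if asymptomatic despite being Grade 3, except for phosphate levels as described above".
- **Hematological list:** "Platelets < 25,000" per microliter (or bleeding below 50,000), "Grade 4 neutropenia lasting 7 or more days", and neutropenic fever.

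Two decision rules use the DLT count. In the lead-in (sections 4.1 and 7.1), one or fewer DLTs in six patients means continue, and two or more means move to the lower dose level. In phase II (sections 7.1 and 7.3), once six patients have been treated, a dose level ends if more than 30% of its patients have DLTs.

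**The concern.** A severity-based definition should not score the worse of two events lower. The general criterion and the electrolyte criterion, the two bullets just above the vomiting bullet, both say Grade 3 or greater; the vomiting bullet says only Grade 3. The list of events not considered DLTs does not explain the gap, since it excuses vomiting only when antiemetics were inadequate.

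The general grading scale in section 5.6 (Assessment of Intensity) ties Grade 4 to an immediate risk of death. Such an event, if isolated, would enter both rules as no DLT. With six patients and a threshold of two, one event can decide whether the starting dose goes forward.

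**Working it through.** **1. Criteria against the event.** Take related, non-fatal Grade 4 vomiting with no other qualifying toxicity.

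| Section 5.6 criterion | Met? |
|---|---|
| General Grade 3 or greater non-hematological | No, vomiting is excluded |
| Electrolytes, Grade 3 or greater | No, none present |
| Nausea/vomiting uncontrolled at 72 hours | No, the bullet says Grade 3 |
| Hy's Law | No |
| Persistent Grade 2 or phosphate-type laboratory problems | No |
| Death | No |

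The event meets no criterion. If Grade 3 in the vomiting bullet is read as a floor, Grade 4 vomiting controlled within 72 hours still escapes. The word isolated matters: an accompanying Grade 3 or greater electrolyte disturbance or other counted toxicity would be a DLT in its own right. So would an episode already at Grade 3 and uncontrolled at 72 hours before it worsened.

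**2. The plan's own figures.** The plan gives no operating characteristics for the DLT rules. Its response rule (12 + 12 patients, stop if fewer than 3 of 12 respond, success if 7 or more of 24) reproduces exactly: type I error 4.87%, power 86.20%, early stopping 73.58% at a 15% response rate and 8.34% at 40%, as in Table 11. The two early-stopping figures are inputs to step 4.

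**3. Lead-in.** Let d be the rate of already counted DLTs and m the rate of isolated omitted events. Both are assumed, the two are mutually exclusive, and all patients are evaluable. With q = d + m when the event counts and q = d as written:

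P(clear) = (1 − q)^6 + 6q(1 − q)^5

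For d = 0.10 as written: 0.5314 + 0.3543 = 0.8857.

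| d | m = 0 (as written) | m = 0.5% | m = 1% | m = 2% |
|---|---|---|---|---|
| 10% | 88.57% | 87.58% | 86.55% | 84.44% |
| 20% | 65.54% | 64.31% | 63.08% | 60.63% |

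The falls are 1.0, 2.0 and 4.1 points at d = 10%, and 1.2, 2.5 and 4.9 points at d = 20%.

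**4. Any toxicity stop at the starting dose.** A stop is two or more DLTs in the first six, or cumulative DLTs/n above 0.30 at any n from 7 to 24, by exact recursion patient by patient. After patient 12, surviving paths are multiplied by one minus the futility-stop probability (0.7358 or 0.0834). Response and DLT are taken as independent.

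| d | True response rate | As written | m = 0.5% | m = 1% | m = 2% |
|---|---|---|---|---|---|
| 10% | 15% | 12.96% | 14.17% | 15.41% | 18.02% |
| 10% | 40% | 13.36% | 14.65% | 15.98% | 18.79% |

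At d = 10% the rise runs from 14.17 − 12.96 = 1.2 points to 18.79 − 13.36 = 5.4 points. At d = 20%, a 40% response rate and m = 2%, the figure goes from 45.8% to 52.9%, about 7 points.

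**5. One omitted event in the lead-in.** If exactly one of six patients has the event, counting it changes the decision when exactly one of the other five has a counted DLT. For m near 0 this is 5 × 0.1 × 0.9^4 = 0.328 at d = 10% and 5 × 0.2 × 0.8^4 = 0.410 at d = 20%. These are conditional figures. The condition itself has probability 6m(1 − m)^5, which is 2.9%, 5.7% or 10.8% at m = 0.5%, 1% or 2%.

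**The case against.** **An investigator would read the vomiting bullet as a floor.** This is plausible, and not counting vomiting that antiemetics control fits the bullet's evident purpose. But neighboring bullets say or greater and this one does not, so the text leaves the matter to interpretation during a six-patient decision.

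**The event is rare, and the plan's evidence raises no alarm.** This stands. Among the 13 patients in section 2.4 given the same combination and dose, nausea had no Grade 3 or greater events. Vomiting is not among the events listed at 20% or more, so it occurred in at most 2 of 13 at any grade. One Grade 3 or greater gastrointestinal event is not itemized, so a zero rate is not shown. Every value of m above is an assumption.

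**Other oversight exists.** This also stands. Life-threatening toxicities are reported immediately (section 5.6), toxicity summaries follow every six evaluable patients, and the IND Office must approve expansion (section 7.3). Table 4 permanently discontinues futibatinib for other Grade 4 adverse reactions. None of this adds to the DLT count, but a reader who inferred that the dose would advance with nobody aware of the event would be going beyond the documents.

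**Anemia.** A reader might infer that leaving out Grade 4 anemia is the same error. It too meets no criterion, although Table 5 describes it as "Grade 4 (life threatening consequences; urgent intervention indicated", and the platelet threshold that does count is itself Grade 4 there ("Grade 4 (PLT < 25,000/mm" cubed). But anemia is absent at every grade from a short closed list, so no lower grade counts while a higher one does not. Table 5 requires a hold and dose reduction, and hematologic support "may be administered as medically indicated". The omission may be deliberate. The same holds for fatigue, which is excluded and never restored.

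**Conclusion.** The inconsistency for vomiting is real and follows from the text alone: as written, the less severe uncontrolled event counts and the isolated Grade 4 event does not, in either DLT rule. Severity is minor. At assumed event rates of 0.5% to 2% and a 10% counted-DLT rate, the lead-in clearance probability moves by about 1.0 to 4.1 points and the chance of any toxicity stop by about 1.2 to 5.4 points, with larger shifts at a 20% DLT rate. These sizes rest on assumed rates, full evaluability, a check of the 30% rule after every patient, and independence of response and DLT. The conditional 33% and 41% figures should not be read as the expected effect.

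The documents do not support extending the finding to anemia or fatigue as errors.

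**What to change.** In section 5.6, replace the nausea and vomiting bullet with: *Grade 4 vomiting, or Grade 3 nausea or vomiting not controlled at 72 hours despite appropriate antiemetic therapy*, keeping the requirement that the event be study-drug related. Because a patient with a DLT is evaluable under section 5.6, this also settles evaluability for the event.

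The cost is a one-line edit and the slightly higher chance of de-escalation or toxicity stopping given above. The response rule's stated type I error and power do not change. A de-escalation adds six lead-in patients, within the stated maximum of 6 + 24 = 30.

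Optionally, the sponsor may add Grade 4 anemia to the hematological list, or say in one sentence that it is left out on purpose.

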6 REGULATORY AND REPORTING REQUIREMENTS

6.1 Evaluation of Toxicity/Adverse Events

Evaluation of toxicity will be done in accordance with the National Cancer Institute's Common Terminology Criteria for Adverse Events (CTCAE) version 5.0 (https://ctep.cancer.gov/protocolDevelopment/electronic_applications/ctc.htm#ctc_50).

All clinically insignificant abnormal laboratory tests will not be documented. Grade 1 toxicities (related or unrelated) will not be collected or documented as these are not considered clinically significant in this patient population and/or they are expected for these study agents. Grade 2 or higher toxicities that are felt to be treatment related and unexpected will be documented. Unless otherwise documented in the electronic medical record as clinically significant and study drug related, all laboratory abnormalities will be assumed to be related to the patient's other co-morbid conditions, prior therapies, other concomitant therapies/medications, or underlying cancer.

The principal investigator is responsible for monitoring the safety of patients who enroll in the study. All AEs occurring after any administration of the study drug will be followed until resolution, stabilization, death, loss to follow up, or commencement of new therapy. The descriptions and grading scales found in the revised NCI CTCAE version 5.0 will be used for adverse event reporting. A copy of the CTCAE version 5.0 can be downloaded from the CTEP web site (<http://ctep.cancer.gov/reporting/ctc.html>).

The investigator (or physician designee) is responsible for verifying and providing source documentation for all adverse events and assigning the attribution for all adverse events for subjects enrolled. Attribution and outcome should be assigned separately for each drug and noted on the CRF.

The Investigator is responsible for completing a toxicity/efficacy summary report, and submitting it to the IND Office Medical Affairs and Safety Group, for review and approval.

Planned interim analyses occur at two time points: one cohort for the lead-in patients after all patients have completed the initial 21 days of study treatment (lead-in cohort summary), and the other for patients who are enrolled to the stage I (stage I cohort summary). The cohort summary should be submitted before study advancing/changing dose levels. A copy of the cohort summary should be placed in the Investigator's Regulatory Binder under "sponsor correspondence".

Causal Relationship with Study Drug

The causal relationship between an AE and study drug will be assessed using the following 2-point scale, taking into account the patient's condition, medical history, concomitant medications, and the temporal relationship between study drug administration and onset of the event, **as well as biological plausibility**.

An AE is considered to be “Related” if the event follows a reasonable temporal sequence from administration of study drug and there is a reasonable possibility that at least one of the following conditions is true:

- A positive dechallenge: This means that the event improves or resolves after the drug is stopped (temporarily or permanently).
- A positive rechallenge: This means that the event reappears after the drug is restarted.
- The event cannot be reasonably explained by the patient’s clinical state and/or other therapies administered.
- A single occurrence of an event that is uncommon and known to be strongly associated with drug exposure (e.g., angioedema, Stevens-Johnson syndrome).

An AE is considered to be “Not related” if there is no reasonable possibility that at least one of the following conditions is true:

- The event occurred prior to study drug administration.
- There is no reasonable possibility that the study drug caused the event. (“no reasonable possibility” means there is no evidence to suggest a causal relationship between the study drug and the AE)
- The event does not follow a reasonable temporal sequence from administration of study drug and could have been produced by a documented pre-existing condition, concomitant medication or patient’s clinical state.

Outcome of Adverse Events

Record the outcome of AEs as follows:

• Resolved	• Not resolved	• Fatal
• Recovered with sequelae	• Recovering	• Unknown

Follow-up of Adverse Events

Any ongoing AEs should be followed until the earliest occurrence of one of the following:

- The AE has resolved or stabilized
- Completion of safety follow-up visit
- Start of new antitumor therapy
- Withdrawal of consent
- Death
- Other (e.g., transfer to another hospital)

Laboratory Assessments

All laboratory results must be reviewed by the Investigator. A new laboratory or instrumental abnormality that has a clinical impact on a patient (including e.g., resulting in study drug dose reduction, treatment delay, treatment discontinuation or requirement of intervention) is considered an AE, unless it is considered part of clinical manifestations to a clinical diagnosis that is already reported as an AE. All laboratory values that are out of the normal range are to be evaluated for their clinical impact before next dosing is given.

Repeat Testing: Evaluation of any clinically significant laboratory test will be repeated, as clinically indicated, until the value returns to the baseline level or clinically stabilizes, or until another treatment is given.

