Safety analysis: All patients who receive therapy will be considered evaluable for safety. Lead-in patients will be monitored for DLT in cycle one. Patients are evaluable if they have received at least 75% of total scheduled study agents in initial 21 days or have experienced a treatment related DLT. Patients are non-evaluable if they meet all the following criteria in cycle one: they have not experienced a treatment-related DLT, they have not received 75% of total scheduled study agents, and therapy is held for logistic and underlying medical issues but not for treatment-related toxicity. Non-evaluable patients may be replaced.

This study will utilize the Common Terminology Criteria for Adverse Events (CTCAE) version 5.0 for adverse event reporting. A copy of the CTCAE version 5.0 can be downloaded from the CTEP home page (<http://www.ctep.info.nih.gov>) and is appended to this protocol. Life-threatening toxicities should be reported immediately to the study chair who, in turn, must notify the IRB. Reporting of adverse reactions does not supplant the reporting of toxicities as part of the results of the clinical trial. Follow-up information should describe whether the event has resolved or continues, if and how it was treated, and whether the patient continued or discontinued study participation. The form and fax confirmation sheet must be retained. Pregnancy follow-up should describe the outcome of the pregnancy, including any voluntary or spontaneous termination, details of the birth, and the presence or absence of any congenital abnormalities or birth defects.

Adverse Event (AE): An AE is defined as any untoward medical occurrence in a clinical study patient and does not necessarily have a causal relationship with the study drug. An AE can therefore be any unfavorable and unintended sign (including an abnormal finding), symptom, or disease temporally associated with the use of a study drug, whether or not related to the study drug. This includes any occurrence that is new in onset or aggravated in severity or frequency from the baseline condition, or abnormal results of diagnostic procedures, including laboratory test abnormalities.

Please note: Progression of the cancer under study is not considered an adverse event.

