All AEs will be collected from the time the ICF is signed through 30 days after the last dose of any study therapy (safety follow-up) or until the start of new antitumor therapy, whichever is earlier. For all AEs that occur between signing ICF, there is no need to record those that are unrelated unless it is mandatory by local regulations. All AEs will be documented in the eCRF. Any untoward medical event that occurs after the safety follow-up is not considered an AE, unless the Investigator considers that the AE is related to the study drug. Serious AEs related to study therapy will be collected through the survival follow-up.

All AEs will be documented in the eCRF. Documentation should include onset and resolution/stabilization dates, severity/grade, relationship to study drug, and outcome of the event.

Signs and symptoms of a pre-existing disease should not be considered an AE, but should rather be considered baseline signs and symptoms. Clinically significant worsening of pre-existing signs and symptoms is considered an AE.

Anticipated day-to-day fluctuations (intermittent) of pre-existing conditions or clinical labs, including the disease under study, need not be considered adverse experiences unless deemed clinically significant, worse than baseline, and at least possibly related to study drug/research procedure. An unexpected adverse drug reaction is an adverse reaction, the nature or severity of which is not consistent with the applicable product information.

Abnormal laboratory findings considered by the reporting investigator to be clinically significant, e.g., those that are unusual or unusually severe for the population being studied or known toxicity of study drug(s) should be documented as adverse events if felt to at least possibly related to study drug/research procedure. AEs may be documented by dictation or toxicity template forms at choice of physician.

Eliciting Adverse Event Information: Adverse events will be elicited at each clinic visit during participation in the study. All adverse events that are directly observed and all adverse events that are spontaneously reported by the patient are to be documented by the investigator. The study chair or physician designee is responsible for determining the attribution of adverse events to study drug.

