All adverse experiences occurring during the study should be documented. At each scheduled protocol visit, patients will be asked a non-leading question to elicit adverse experiences. Adverse experiences should be documented in terms of a medical diagnosis if possible. When this is not possible, the adverse experience should be documented in terms of signs and/or symptoms observed by the Investigator (death is not an AE; death is an outcome).

At each scheduled protocol visit/assessment, the Investigator or designee will evaluate adverse experiences. The description of the event should include:

- Description of each adverse experience (diagnosis whenever possible).
- Date of onset and resolution (and time, where appropriate).
- Timing (i.e., intermittent, continuous).
- Maximum intensity with final decision made by attending physician if there are differing assessments.
- Causality should be assessed initially at the best knowledge of the investigator, especially when a SAE has occurred with minimal information available, and may be re-assessed at a later time after subsequent labs, tests, physical exam, etc. If there is a difference in opinion of causality between practitioners, the attending physician or PI attribution will be final determinant. There may be situations when an SAE has occurred and the investigator has minimal information to include in the initial report to the sponsor. However, it is very important that the investigator always makes assessment of causality for every event prior to transmission of the SAE report/eCRF to the sponsor. The investigator may change his/her opinion of causality in light of follow-up information, amending the SAE report/eCRF accordingly. The causality assessment is one of the criteria used when determining regulatory reporting requirements.

The Investigator is responsible for assessing the severity of the AE and/or the ADE, the causal relationship between any events and the clinical study procedure, activities or device. Additionally, the Investigator is responsible for providing appropriate treatment for the event and for adequately following the event until resolution.

Attribution - the determination of whether an adverse event is related to a medical treatment or procedure.

- **Definite** - the adverse event is clearly related to the investigational agent(s).
- **Probable** - the adverse event is likely related to the investigational agent(s).

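### Sections 5.6 and 6.1 give incompatible recording rules for adverse events, a primary endpoint: related Grade 1 events are required by one and barred by the other

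*Combined protocol and SAP*

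**What the plan says.** Section 1.2 makes adverse events, clinical and laboratory, a primary endpoint without limit of grade or expectedness. Section 7.2 plans descriptive statistics by grade, type and dose level.

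Section 5.6 leans toward full recording. It says "All AEs will be documented in the eCRF" and "All adverse experiences occurring during the study should be documented", and warns that "Reporting of adverse reactions does not supplant the reporting of toxicities as part of the results of the clinical trial". It then directs that events be recorded by the Phase II entries of Table 10. In the three related rows of that table (possible, probable, definitive), every legible cell includes Phase II, Grade 1 among them. In the unrelated and unlikely rows, Phase II appears from Grade 3 upward. Expectedness plays no part. Section 6.4 adds that adverse events are entered in the electronic case report form.

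Section 6.1 reads differently. "Grade 1 toxicities (related or unrelated) will not be collected or documented", on the ground that such events are not clinically significant in this population and/or are expected. Next, "Grade 2 or higher toxicities that are felt to be treatment related and unexpected will be documented". Unless the medical record marks them as clinically significant and drug related, "all laboratory abnormalities will be assumed to be related to the" patient's other conditions, other treatments or cancer. Yet the same section makes the investigator responsible for "verifying and providing source documentation for all adverse events" and for their attribution, and says "Attribution and outcome should be assigned separately for each drug and noted on the CRF".

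**The concern.** The recording rule decides what is in the database when a primary endpoint is summarised. Events that were never collected may not be recoverable at analysis. If sites work from the recording sentences of Section 6.1, related Grade 1 events are absent and expected related events of Grade 2 or higher may be. Both omissions push the toxicity profile the same way, toward better apparent tolerability.

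That direction matters here. The trial is motivated by the wish for a better tolerated regimen than lenvatinib plus pembrolizumab, for which Section 2.4 cites treatment-related events of any grade in 97% of patients and of Grade 3 or 4 in 67%. Without related Grade 1 events, no any-grade figure comparable with the 97% could be produced. If expected events were also left out, the figure to set beside the 67% would be too low as well.

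**Working it through.** No sample-size or power figure underlies this point, so the check is a comparison of rules by class of event.

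| Class of event | Section 5.6, Table 10 (Phase II) | Section 6.1, recording sentences |
|---|---|---|
| Related, Grade 1 | record | not collected |
| Related, Grade 2 or higher, unexpected | record | document |
| Related, Grade 2 or higher, expected | record | not mentioned |
| Unrelated or unlikely, Grade 3 to 5 | record | not mentioned |
| Unrelated or unlikely, Grade 2 | not required | not mentioned |
| Unrelated or unlikely, Grade 1 | not required | not collected |

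Reading down the table:

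1. The first row is a direct contradiction. Expectedness does not remove it, because neither rule uses expectedness at Grade 1.
2. The second row is the only one in which both sections give the same positive instruction.
3. In the third row, Section 5.6 requires the events and Section 6.1 is silent. Its sentence does not say that only unexpected events are documented, so it does not bar expected ones. A site working from Section 6.1 nevertheless finds no specific instruction to record them.
4. In the last two rows, Table 10 asks for nothing in Phase II, while the all-events sentences of Section 5.6 ask for everything. Section 5.6 is therefore not fully consistent with itself either.

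Several classes have their own rules and lie outside the gap:

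- Serious events are reported whether expected or not (Section 6.2).
- Grade 3 and 4 eye toxicities are reported as serious (Section 6.2).
- Dose-limiting toxicities are assessed separately (Section 5.6).
- Laboratory abnormalities with clinical impact count as AEs (Section 6.1, Laboratory Assessments).

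What remains exposed is chiefly the non-serious, symptomatic, related event.

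To see which events those are, take the combination study in Section 2.4, Table 2 (N = 13):

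- Nausea: 8/13 = 61.5%; Grade 3 or higher 0; worst grade 1 or 2 in 8 − 0 = 8 patients.
- Diarrhea: 7/13 = 53.8%; Grade 3 or higher 0; worst grade 1 or 2 in 7 − 0 = 7 patients.
- Stomatitis: 6/13 = 46.2%; Grade 3 or higher 0; worst grade 1 or 2 in 6 − 0 = 6 patients.

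Section 2.2 lists all three among the frequent treatment-related events of futibatinib. Hyperphosphatemia (12/13 = 92.3%) is left out of the illustration because the separate laboratory rule may bring it back.

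The counts are regardless of relationship, are not split between Grades 1 and 2, and carry no classification of expectedness. They show which events are exposed and do not measure the loss, so they are not scaled to this trial.

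**The case against.** The strongest reply is that the plan, read as a whole, already requires fuller recording. Section 5.6 says so more than once, Section 6.4 sends adverse events to the case report form, and silence in Section 6.1 does not cancel a positive instruction elsewhere. For expected events of Grade 2 or higher this is right. A reader might infer that Section 6.1 forbids recording them or that no rule covers them. The documents do not support either reading, and downward bias from this source arises only where a site works from Section 6.1 alone. For related Grade 1 events the reply fails, because Section 6.1 is not silent: it excludes them. Table 10 is titled as a recommendation, but the sentence that invokes it is mandatory.

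A second reply is that Section 6.1 gives a reason for a Grade 2 threshold, that no any-grade related rate is planned by name, and that the choice is the sponsor's. It is true that the contradiction calls only for one governing rule. But Section 7.2 summarises toxicity by grade, and Section 1.2 sets no lower limit.

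Two further inferences are tempting and should not be drawn:

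- **Lead-in decision.** One might argue that presuming laboratory abnormalities unrelated could turn two dose-limiting toxicities among six lead-in patients into one. The presumption can be rebutted by a record entry. Section 5.6 requires electrolyte toxicities to be clinically significant, excludes asymptomatic Grade 3 laboratory results other than phosphate, and makes persistent Grade 2 phosphate abnormalities a matter for agreement between the treating physician and the principal investigator. Section 6.1 has every laboratory result reviewed. The documents show no route by which such an event would be lost.
- **Causality scales.** Section 5.6 uses five attribution levels, Section 6.1 two and Section 6.5 three. One might infer that Table 10 cannot be applied without the five. For Phase II it turns only on related versus not related, so the two-level scale is enough. Aligning the scales is tidying.

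**Conclusion.** The concern holds. Sections 5.6 and 6.1 contradict each other on related Grade 1 events. They also leave a site working from Section 6.1 without a specific instruction on non-serious, expected, related events of Grade 2 or higher, although Section 5.6 requires them. No text sets an order of precedence.

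The direction of the effect is clear: following Section 6.1 understates toxicity. Its size cannot be derived from the documents. It depends on which section sites follow, on the Grade 1 versus Grade 2 split, and on which events are deemed related and expected. The conclusion rests on the legible cells of Table 10 and on taking Section 6.1 at its word. The two-stage efficacy design is unaffected. Because the matter determines the content of a primary endpoint, it must be corrected prospectively.

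**What to change.** In Section 6.1, delete the sentence excluding Grade 1 events and the restriction to related and unexpected events. Replace them with: *AEs are recorded in the eCRF at least according to the Phase II cells of Table 10; expectedness does not affect recording and is used only for expedited reporting.*

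For laboratory abnormalities that qualify as AEs (clinically significant under Section 5.6, or with clinical impact under the Laboratory Assessments part of Section 6.1), state that relationship is assessed by the causality criteria in Section 6.1 and is not presumed absent.

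State also whether the all-events sentences in Section 5.6 extend to unrelated or unlikely Grade 1 and 2 events, which Table 10 does not require in Phase II. If the sponsor prefers a Grade 2 threshold, Table 10 and the all-events sentences must be changed to match, and the safety summary should state the limit.

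The cost is protocol wording and more data entry than Section 6.1 implies, although Section 5.6 already requires it. Reported toxicity rates will be higher than under Section 6.1.
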